### **1.2.10 Potential Risks and Benefits**

The safety risks of DSF are well established based on over 60 years of clinical use [18,37,66]. From 1968 to 1991, 154 adverse drug reactions were reported to the Danish Committee on Adverse Drug Reactions: hepatic (34%), neurological (21%), cutaneous (15%), psychiatric (4%), and other (26%). However, some patients may have received much higher doses than the currently approved dosage and may have consumed alcohol while taking DSF. Rate of adverse event is estimated to be one per 200-2000 patients per year [67]. The more common and mild side effects include: drowsiness, usually of short duration (can be managed by taking

medication in the evening); headache; nausea and vomiting; metallic or garlic-like aftertaste; allergic dermatitis; impotence; DSF-ethanol reaction after ingestion of alcohol (flushing, headache, nausea, sweating, palpitation, dyspnea, tachycardia, hypotension, and rarely cardiovascular collapse). These symptoms are generally transient and typically resolve within first two weeks. DSF-ethanol reaction can be avoided by abstinence from drinking alcohol, and case reports of fatal DSF-ethanol reaction in the past occurred with much higher doses of DSF. Other rare but more severe toxicities include: hepatotoxicity or hepatitis, typically reversible if DSF is discontinued early (should be followed with liver function tests); peripheral neuropathy; optic neuritis; extrapyramidal symptoms; psychosis. Patients with hepatic dysfunction, active pregnancy, and idiopathic seizure disorder should not be given DSF.

As discussed in Section 1.2.6, our previous phase 1 study of DSF in combination with adjuvant TMZ established 500 mg of DSF per day as the MTD. At this dose, most patients tolerated DSF with adjuvant TMZ well, but 2 of 7 patients developed dose-limiting confusion and motor neuropathy after prolonged administration. Possible or probable DSF-related toxicities were all neurological and were mostly self-limiting or reversible. The investigators and patients should pay particular attention of any early signs of the neurological symptoms seen in the previous phase I study including delirium, ataxia, and neuropathy, but careful workup to rule out tumor progression or other causes should also be considered before attributing those symptoms to DSF.

Given its long track record of safety when used alone, especially below 1000 mg, DSF should pose minimal risk when given to presumed GBM patients before their surgical resection. Although patients without histological confirmation would qualify for this study, a misdiagnosis of GBM based on MRI finding is relatively uncommon. Furthermore, since it is not a cytotoxic chemotherapy, a short-course administration of pre-operative DSF for 3 days to a patient with a different diagnosis should not adversely affect his/her subsequent treatment. As for overlapping toxicity with TMZ or RT, DSF appears to have preferential inhibition of tumor MGMT versus liver MGMT *in vitro*, and our previous phase I study demonstrated safety when combining it with TMZ. Since DSF may be radiosensitizing due to its possible effect on DNA repair based on *in vitro* studies, its tolerability with RT is currently unknown. To monitor for severe toxicity, patients will be followed frequently during RT with weekly clinical evaluation and CBC. Liver function test will be checked before starting DSF, and every month while taking DSF.

### 1.2.11 Potential Adverse Events Related to DSF

MedDRA Term	Frequency: Likely: greater than 10% Less Likely: 1-10% Rare: 1% or less
Neoplasms	Rare: Tumor necrosis
Blood and lymphatic system disorders	Rare: Neutropenia, anemia, leukopenia, thrombocytopenia, lymphopenia (likely due to TMZ)
Immune system disorders	Rare: Hypersensitivity
Metabolism and nutrition disorders	Likely: Alcohol intolerance, metallic or garlic-like aftertaste
Psychiatric disorders	Less Likely: psychosis, delirium (need to rule out tumor progression)
Nervous system disorders	Likely: Drowsiness, headache, confusion Less Likely: ataxia, gait disturbance, peripheral neuropathy Rare: Extrapyramidal symptoms
Eye disorders	Less Likely: Optic neuritis
Cardiac disorders	Less Likely: Tachycardia, hypotension (need to rule out DSF-alcohol reaction)
Respiratory, thoracic, and mediastinal disorders	Less Likely: Dyspnea (need to rule out DSF-alcohol reaction)
Gastrointestinal disorders	Likely: Nausea, vomiting, diarrhea Less Likely: constipation (likely due to TMZ)
Hepatobiliary disorders	Rare: Hepatitis
Skin and subcutaneous tissue disorders	Less Likely: Allergic dermatitis
Musculoskeletal	Rare: Arthralgia, myalgia
Renal and urinary disorders	Rare: Dysuria, hematuria
Reproductive system	Less likely: impotence
General disorders	Likely: Fatigue

### 1.3 Study Rationale

Preclinical *in vitro* studies have identified DSF as a promising and selective drug against GBM cells. *In vivo* experiments have showed synergistic effect of DSF with RT and TMZ against orthotopic GBM models. Given its well-established safety profile, excellent penetration across the blood brain barrier, relatively low cost, and ease of administration with an oral formulation, the potential of DSF to enhance the efficacy of RT and TMZ for GBM warrants clinical trial investigation. We have previously demonstrated the feasibility

and safety of combining DSF with adjuvant TMZ after RT and concurrent TMZ. Adding DSF to RT and concurrent TMZ in the initial treatment GBM is a rational next step to test the potential of DSF to improve clinical outcome of GBM patients. Since Cu has been shown in the preclinical studies to be crucial for the activity of DSF, patients will also take Cu TID with meals to maximize the biological activity of DSF. Therefore, the purpose of this study is to identify the optimal dose of DSF to combine with RT and TMZ.

The proposed study will be a single arm, phase I/II study of DSF/Cu in combination with adjuvant standard RT and TMZ for patients with newly diagnosed GBM. There will be an optional phase 0 pharmacokinetic study where patients will take 3 days of DSF/Cu prior to their surgery to allow for collection of blood and tumor samples during surgery for analysis of drug uptake.

As for the rationale for the proposed expansion cohort, this is based on the promising finding of the dose-escalation phase of the study. After enrollment of the 18 patients for the dose-escalation phase, 8 patients were treated with DSF of 250 mg/day (dose level 2) and 10 patients with 375 mg/day (dose level 3). Three dose-limiting toxicities (DLTs) were observed: 1 with 250 mg/day (grade 2 urinary incontinence and ataxia), and 2 with 375 mg/day (both grade 3 elevated liver enzymes). The TITE-CRM model estimated the DLT probability of DSF to be 10% (95% CI: 3-29%) at 250 mg/day, and 21% (95% CI: 7-42%) at 375 mg/day. Thus, we have declared that the MTD of DSF in combination with RT/TMZ/Cu for GBM is 375 mg/day, and the recommended phase II dose is 250 mg/day. Furthermore, tumor mutations were evaluated with next-generation sequencing for all patients to explore possible biomarkers for response. Notably, GBM patients with *IDH* (n = 6), *BRAF* (n = 2), and *NF1* (n = 1) mutations exhibited much better PFS and OS than those without these mutations (n = 9): 1-year PFS of 100% vs 22%, respectively, p = 0.001; 1-year OS of 100% vs 42%, respectively, p = 0.006. Given that the historical PFS and OS of newly diagnosed GBM patients treated with RT and TMZ is approximately 27% and 60% at one year [4], respectively, the preliminary data of this molecular subset of GBM are thought-provoking and raise the possibility that these mutations make GBM tumors more sensitive to DSF/Cu in combination with chemoradiotherapy. Interestingly, all three mutations, which affect approximately 15-20% of GBM tumors, make tumor cells more dependent on glutamate for cellular metabolism [68-70]. As DSF metabolite can affect glutamate uptake, this may be the biological mechanism for the improved outcomes for GBM with these mutations. Thus, we have proposed to add an expansion cohort to this phase I/II study to treat additional GBM patients with *IDH*, *BRAF*, or *NF1* mutations to increase the statistical power of our preliminary finding.

## 2.0 OBJECTIVES AND ENDPOINTS

Objectives	Endpoints

Primary
 
Dose-escalation Phase: To determine the maximum tolerated dose (MTD) or the recommended phase 2 dose (RP2D) of disulfiram (DSF) when administered with concurrent radiation therapy (RT) and temozolomide (TMZ) in patients with newly diagnosed glioblastoma (GBM).
 
Dose-expansion Phase: To evaluate the OS of the molecularly-defined cohort of newly diagnosed GBM with IDH, BRAF, or NF1 mutations when treated with the combination of DSF/Cu plus concurrent RT and TMZ.
	
Dose-escalation Phase: The maximum tolerated dose (MTD) of DSF with concurrent RT+TMZ will be defined as the dose associated with a 20% probability of dose-limiting toxicity (DLT). Toxicity will be coded using CTCAE version 4.0, and DLT will be defined as toxicity that occurs within 18 weeks from the first day of RT and is possibly, probably or definitely related to DSF/Cu (or 12 weeks from the completion of RT if there is a delay/interruption of RT).
 
Dose-expansion Phase: For the expansion cohort of GBM with IDH, BRAF, and NF1 mutations, the overall survival (OS) of this molecularly-defined cohort will be measured from the first day of RT.

Secondary
 

1. To describe the toxicities of DSF when given concurrently with RT and TMZ.

2. To evaluate the PFS of the molecularly-defined cohort of newly diagnosed GBM with IDH, BRAF, or NF1 mutations when treated with the combination of DSF/Cu plus concurrent RT and TMZ

3. To determine the active DSF metabolite concentration in plasma and tumor tissues.

	

1. The adverse events will be graded by NCI CTCAE version 4.0.

2. Progression-free survival (PFS) will be determined from the first day of RT to the time of tumor progression or death, whichever occurs first. Tumor progression will be determined using the RANO criteria.

3. Intratumor and plasma concentration of DSF metabolite (ditiocarb-copper complex) will be determined using mass spectrometer method.


Tertiary/Exploratory
 

1. To estimate rate of pseudo-progression after chemoradiotherapy

2. To explore the pharmacodynamics effect of DSF on glutamate metabolism in plasma and tumor tissues

	

1. Pseudo-progression is defined as a transient increase of tumor after chemoradiotherapy that subsequently stabilizes without a change of therapy

2. Pharmacodynamics studies on glutamate metabolism will include measurement of glutamine, glutamate, aspartate, glucose, and lactate levels in blood and tumor tissues using mass spectrometry method.

## 3.0 PATIENT SELECTION

### 3.1 Inclusion Criteria

1. Diagnosis of GBM or its histological variants (WHO grade IV). Patients who are participating in the optional pre-operative pharmacokinetic study may have presumed GBM based on clinical/radiological findings. However, patient must have histologically confirmed GBM before continuing to receive DSF with concurrent RT/TMZ.
2. Expansion Cohort: must have a diagnosis of GBM (or its histological variants) with *IDH*, *BRAF* or *NF1* mutations. Confirmation of these mutations may be either by immunohistochemistry or next-generation sequencing.
3. At least 18 years of age.
4. Karnofsky performance status (KPS) of at least 60% (see Appendix A).
5. For patients who will participate in the optional DSF pharmacokinetic study, they should be eligible for surgical resection for which at least 0.2 cubic cm or approximately 200 mg of tumor will be removed in addition to tumor specimen required for pathology evaluation. Patients enrolled after undergoing surgical resection or biopsy with histologically confirmed GBM are not required to meet this point of inclusion.
6. Eligible for and planning to receive standard fractionated RT with concurrent TMZ.
7. Willing to remain abstinent from consuming alcohol while on DSF.
8. Willing to defer definitive surgery for one week while taking DSF and Cu. Patients who declined the optional pre-operative pharmacokinetic study or enrolled after undergoing surgical resection or biopsy with histologically confirmed GBM are not required to meet this point of inclusion.
9. Meets the following laboratory criteria:
  - a. Absolute neutrophil count  $\geq$  1,500/mcL
  - b. Platelets  $\geq$  100,000/mcL
  - c. Hemoglobin  $>$  10.0 g/dL (transfusion and/or ESA allowed)
  - d. Total bilirubin  $\leq$  2x institutional upper limit of normal (ULN)
  - e. AST and ALT  $<$  3 x ULN
  - f. Serum creatinine  $<$  1.5 x ULN or creatinine clearance  $>$  50 mL/min (by Cockcroft-Gault)
10. Females of childbearing potential (defined as a female who is non-menopausal or surgically sterilized) must be willing to use an acceptable method of birth control (i.e., hormonal contraceptive, intra-uterine device, diaphragm with spermicide, condom with spermicide, or abstinence) for the duration of the study. Should a woman become pregnant or suspect she is pregnant while participating in this study, she must inform her treating physician immediately.

11. Able to take oral medication.
12. Able to understand and willing to sign an IRB-approved written informed consent document (legally authorized representative permitted).

### **3.2 Exclusion Criteria**

1. Receipt of any other investigational agents within 14 days prior to study treatment.
2. Enrolled on another clinical trial testing a novel therapy or drug.
3. History of allergic reaction to DSF or Cu.
4. Treatment with the following medications are contraindicated with DSF when taken within 7 days prior to the first dose of DSF + Cu: metronidazole, isoniazid, dronabinol, carbocisteine, lopinavir, paraldehyde, ritonavir, sertraline, tindazole, tizanidine, atazanavir. (Note: the following medications are not contraindicated but should be cautioned if taking concurrently with DSF: warfarin, phenytoin, theophylline, chlorzoxazone, chlordiazepoxide, diazepam. If the patient is taking warfarin, INR should be monitored closely. If the patient has to remain on phenytoin, its serum concentration and response should be monitored closely.)
5. Active or severe hepatic, cardiovascular, or cerebrovascular disease, including myocardial infarction within 6 months prior to enrollment, New York Heart Association (NYHA) Class III or IV heart failure (Appendix B), uncontrolled angina, severe uncontrolled ventricular arrhythmias, or electrocardiographic evidence of acute ischemia or active conduction system abnormalities.
6. History of idiopathic seizure disorder, psychosis, or schizophrenia.
7. History of Wilson's disease or family member with Wilson's disease.
8. History of hemochromatosis or family member with hemochromatosis.
9. Pregnant and breastfeeding women will be excluded because of the known teratogenic effect of RT and the unknown effect of TMZ and DSF on fetal development. Women of childbearing potential must have a negative pregnancy test within 14 days of initiation of treatment.

### **3.3 Inclusion of Women and Minorities**

Both men and women and members of all races and ethnic groups are eligible for this trial.

## **4.0 PATIENT REGISTRATION**

**Patients must not start any protocol intervention prior to registration through the Siteman Cancer Center.**

The following steps must be taken before registering patients to this study:

1. Confirmation of patient eligibility
2. Registration of the patient in the Siteman Cancer Center OnCore database
3. Assignment of unique patient number (UPN)

### **4.1 Confirmation of Patient Eligibility**

1. Confirm patient eligibility by collecting the information listed below: Registering MD's name
2. Patient's race, sex, and DOB
3. Three letters (or two letters and a dash) for the patient's initials
4. Copy of signed consent form
5. Completed eligibility checklist, signed and dated by a member of the study team
6. Copy of appropriate source documentation confirming patient eligibility

### **4.2 Patient Registration in the Siteman Cancer Center OnCore Database**

All patients must be registered through the Siteman Cancer Center OnCore database.

### **4.3 Assignment of UPN**

Each patient will be identified with a unique patient number (UPN) for this study. All data will be recorded with this identification number on the appropriate CRFs.

## **5.0 TREATMENT PLAN**

### **5.1 Pretreatment Evaluation**

Prior to enrollment, patient must have a complete history, physical examination, evaluation of performance status (KPS), baseline laboratory studies (CBC, BMP, and LFTs), and MRI. For the expansion cohort, patients must have confirmed diagnosis of GBM with *IDH*, *BRAF*, or *NF1* mutations. Diagnosis will be confirmed through the pathology report as a part of standard of care. Although for the dose-escalation phase, there was an optional pre-operative disulfiram study before the initial surgery, this will no longer be applicable for the expansion cohort and has been removed.

## **5.2 Radiation Therapy**

RT should start approximately 4-6 weeks after surgery (up to 8 weeks is permissible). Standard fractionated RT to 60 Gy in 30 daily fractions will be administered in this study. Gross tumor volume (GTV) is defined as T1 contrast enhancing abnormality and surgical cavity. Clinical tumor volume 1 (CTV1) is defined as GTV with a margin of 1.5 cm. Clinical tumor volume 2 (CTV2) is defined as GTV with a margin of 0.5-0.7 cm. CTVs may be modified to respect natural barriers such as bone or tentorium. CTV1 and CTV2 should be expanded uniformly by 0.3-0.5 cm into planning target volume 1 and 2 (PTV1 and PTV2), respectively to account for setup uncertainty. PTV1 should be treated to 46 Gy in 23 fractions of 2 Gy each, and PTV2 should be boosted to an additional 14 Gy in 7 fractions of 2 Gy each for a cumulative total dose of 60 Gy in 30 fractions of 2 Gy each. 3D conformal RT (3DCRT) and intensity modulated RT (IMRT) are all permitted for RT delivery.

## **5.3 Concurrent Temozolomide Treatment**

Concurrent TMZ will be administered continuously (Monday through Sunday) from Day 1 of RT to the last day of RT at a daily oral dose of 75 mg/m^2 for a maximum of 49 days as per standard clinical care. TMZ should be taken before RT. The drug should typically be administered orally at least 1 hour before breakfast every morning. TMZ should not be taken within one hour of DSF and Cu administration. Patients will be instructed to bring all unused drug and the completed medication diary (Appendix C) to each study visit for assessment of compliance.

## **5.4 Disulfiram and Copper Administration during Chemoradiotherapy**

DSF and Cu will be administered during chemoradiotherapy as per dose escalation instructions in Section 5.10. For patients enrolling in the expansion cohort, the dose of DSF will be 250 mg/day. During chemoradiotherapy, DSF should be taken in the morning with approximately 8 ounces of water approximately 1 hour after breakfast, and 2 mg of Cu gluconate should be taken TID with meals but not concurrently with DSF. The rationale of giving Cu in 3 doses is to maintain relatively constant plasma copper throughout the day while DSF is absorbed and metabolized. Concurrent DSF during chemoradiotherapy is administered in the morning to provide the maximum radiosensitizing effect. DSF and Cu should not be taken within one hour of TMZ administration. If the patient misses a dose, s/he should be instructed not to make up that dose but should instead resume dosing with the next scheduled dose. Patients will be instructed to bring all unused drug and the completed medication diary (Appendix D) to each study visit for assessment of compliance.

Medication Schedule	
TMZ	At least 1 hour before breakfast and before RT, but not within 1 hour of DSF + Cu
DSF	1 hour after breakfast
Cu	With breakfast, lunch, and dinner

## **5.5 Laboratory Studies and Tissue Collection during Chemoradiotherapy**

Routine laboratory studies (CBC, BMP, and LFTs) will be obtained before the start of chemoradiotherapy and weekly (for CBC) and monthly (for BMP and LFTs) during chemoradiotherapy or more frequently as clinically indicated. If, during chemoradiotherapy treatment, the patient develops disease progression and undergoes surgical resection of the glioblastoma, a portion of the tissue removed during surgery and along with blood will be archived for future research purposes (please refer to Section 9.0).

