### **6.2.1 Administration of DSF to Patients with Abnormal Hepatic Function**

DSF/Cu should only be administered if hepatic function is within the parameters established in the eligibility criteria. Hepatic toxicity from DSF/Cu is uncommon but may occur. Therefore, hepatic dysfunction that occurs while the patient is on study should prompt an evaluation to determine the cause, including the possibility of hepatotoxicity from concurrent medications including TMZ.

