13. For patients consented for the optional preoperative DSF, eligibility must be reconfirmed after surgery and before the start of RT. For patients consented after surgery, they need to meet eligibility prior to RT.
14. RT and TMZ will start 4-6 weeks after resection (up to 8 weeks is permissible)
15. 30 fractions of RT given over 6 weeks
16. The patient will be followed for 30 days after the last dose of disulfiram for adverse events; 2 years after coming off study, a review of the patient's medical records will be conducted to collect data on progression and survival
17. If the tumor recurs during the 6-month treatment period and the patient has surgery, we will request a portion of the tissue removed during surgery for future correlative studies

18. OPTIONAL; patients whose disease recurs and who will undergo another resection may opt to take p 5 days (+/- 2 days) of preoperative DSF (250 mg per day in the morning) and Cu (2mg PO TID with meals) until the day before the planned surgery. Patient should not take DSF/Cu on the day of surgery.

19. Simulation MRI can be used as pre-RT MRI if conducted with and without contrast

20. Monthly during RT + TMZ.

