### **10.2 Dose-expansion phase:**

Baseline evaluations, labs and MRIs must be done no more than 30 days prior to the start of the protocol therapy.

	B/I	Wks 1-6 	Adjuvant TMZ  Cycles						F/U 	Optional: Tissue collection at recurrence 
			1	2	3	4	5	6		
Informed consent	X									X
Physical exam	X	X 	X	X	X	X	X	X		
KPS	X									
CBC	X	X 	X	X	X	X	X	X		
BMP	X	X 	X	X	X	X	X	X		
LFTs	X	X 	X	X	X	X	X	X		
β-hCG 	X									
MRI w/ and w/o contrast	X 			X		X		X		
Path. diagnosis of GBM with IDH, BRAF, or NF1 mutations	X									
RT		X 								
Temozolomide		X 	X 	X 	X 	X 	X 	X 		
DSF		X 	X 	X 	X 	X 	X 	X 		X 
Cu 		X	X	X	X	X	X	X		X 
Review of medication diary		X 								X
Adverse events		X 	X 	X 	X 	X 	X 	X 	X	X
Collection of tumor										X 
Collection of blood										X 

1. RT and TMZ will start 4-6 weeks after resection (up to 8 weeks is permissible)
2. Adjuvant TMZ will start 4-6 weeks after the end of RT and will be given for 6 28-day cycles
3. The patient will be followed for 30 days after the last dose of disulfiram for adverse events; 2 years after coming off study, a review of the patient's medical records will be conducted to collect data on progression and survival
4. If a patient develops recurrence and is eligible for salvage surgery, he/she will be eligible for optional tissue collection at time of salvage surgery. If he/she is not on DSF/Cu any more, he/she may opt to take 5 days (+/- 2 days) of preoperative DSF and Cu before the planned surgery.
5. Weekly during RT + TMZ
6. Monthly during RT + TMZ.
7. Women of childbearing potential only
8. Simulation MRI can be used as pre-RT MRI if conducted with and without contrast
9. 60 Gy in 30 fractions
10. 75 mg/m^2 daily during RT
11. Days 1-5 of every 28-day cycle
12. DSF is taken in the morning approximately 1 hour after breakfast. The dose of DSF in the expansion cohort is 250 mg once daily during RT.
13. DSF dose during adjuvant TMZ will be 500 mg once daily
14. 2 mg TID with meals while taking DSF

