#### 14.3.2 TITE-CRM Design for the Dose-escalation Phase

The starting dose can have a large impact on the properties of the design. After the trial is completed, most information about the MTD will be obtained if many patients are treated at or near the MTD, thus the sooner the choice of dose can converge on the MTD the more effective the trial will be. However, with concerns about safety we will start at the one dose level lower than the expected MTD. Therefore, our starting dose for this trial will be 250 mg PO daily.

The next thing to be considered is the dose escalation rules. For this trial, we will only allow a single dose level escalation per new patient enrolled on the trial. Therefore, if the previous patient was treated at dose level,  $d_k$ , then a new patient can only be treated at dose levels  $d_{k+1}$  or lower. In order to determine at which level to treat the new patient, we will use a non-weighted, cumulative time of exposure approach. The total length of follow-up for DLT for any patient is 18 weeks. In order to efficiently and effectively determine the MTD, we allow for a dose change when the cumulative time of exposure is 18 weeks. Also, since previously published data shows that toxic events occur evenly throughout the time of the study we will not implement a weighting function. The dose for the next patient is selected so that the estimated probability at that dose is close to the target level. A feature of the dose escalation part of the TITE-CRM program is the flexibility in specifying the margin for the dose selection. This allows the selection of the dose level for the next patient that may have an estimated probability of toxicity larger than the target level but less than the target level plus the margin. It finds the dose closest to the target probability even if it has a higher estimated probability. For this trial we set the admissible margin to be 5%, therefore, the MTD will be chosen as the dose that yields a posterior toxicity estimate closest to 20% while being between 15% and 25%. The admissible margin is also used to help determine stopping rules for the trial. In order to account for the possibility of poor initial outcomes we will employ a run-in of 6 patients, meaning that the minimum number of treated patients will be 6. If after these 6 patients, or any other time during the trial, the lowest dose level has a posterior probability higher than 25% then the trial will stop.

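### Liver tests are scheduled about once in six weeks of DSF with RT and not at its end, so short-lived hepatic DLTs, and late-starting ones that clear before cycle 1, can go undetected

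*Combined protocol and SAP*

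**What the plan says.** - **Schedule during RT.** Section 5.5 sets tests before chemoradiotherapy and then "weekly (for CBC) and monthly (for BMP and LFTs) during chemoradiotherapy or more frequently as clinically indicated". Both calendars agree: "Monthly during RT + TMZ" (10.1 note 20, and the same in 10.2 note 6). Section 1.2.10 is consistent with this: "Liver function test will be checked before starting DSF, and every month while taking DSF".
- **Length of the period.** "30 fractions of RT given over 6 weeks" (10.1 note 15), with DSF daily throughout.
- **Next scheduled liver test.** Neither calendar has a column between weeks 1-6 and adjuvant cycle 1, which starts 4-6 weeks after RT ends. No end-of-RT liver test is listed.
- **Liver values as DLTs.** Under 5.9.2, total bilirubin above 2.0 x ULN, or AST or ALT above 3.0 x ULN, is a DLT. These match the entry limits in 3.1 (bilirubin at most 2 x ULN; AST and ALT below 3 x ULN).
- **Condition for dosing.** Section 6.2.1: "DSF/Cu should only be administered if hepatic function is within the parameters established in the eligibility criteria".
- **What was observed.** Section 1.3 reports three DLTs among 18 patients: one at 250 mg/day (not hepatic) and "2 with 375 mg/day (both grade 3 elevated liver enzymes".
- **Expansion phase.** The same liver-test schedule applies to the 15 further patients planned in 14.3.5. Describing toxicity is a secondary objective (2.0), and neither 6.2 nor 7.4 limits DLT evaluation to dose escalation.

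**The concern.** A laboratory DLT can be recorded only if blood is drawn while the value is abnormal. The plan makes liver values a DLT criterion and a condition for dosing, then measures them about once in the period when the tested dose is given. CBC, by contrast, is drawn weekly. Extra tests are allowed when clinically indicated, but an elevation without symptoms gives no clinical prompt.

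Two things are at stake. One is how completely hepatic toxicity is ascertained, in the reported escalation results and in the expansion cohort. The other is whether the condition in 6.2.1 can be applied in the last weeks of RT, since the protocol does not say which liver result, or how recent a one, satisfies it.

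There is also an attribution problem. Section 5.9.2 excludes events assessed as related to adjuvant DSF. The calendars do not fix the day within cycle 1 on which the test is done. An elevation that began late in RT but is first seen once adjuvant DSF has started could therefore be attributed to the adjuvant course.

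**Working it through.** **1. The plan's own estimate.** Inputs: 1 DLT in 8 patients at 250 mg/day and 2 in 10 at 375 mg/day (1.3); prior estimates 0.05, 0.10, 0.20, 0.30 (14.3.1). The working model and prior are not given, so several one-parameter power and logistic models were tried, with all patients at full weight. Plug-in estimates are 10.5-11.4% and 20.7-22.0%, against the stated 10% and 21%. Intervals are about 2-30% and 6-44%, against 3-29% and 7-42%. The stated figures reproduce.

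**2. Draw times.** Count weeks from the start of RT, which ends at week 6. Assume the monthly draw is at week 4. The cycle 1 draw is at T = 6 + 4 = 10 to 6 + 6 = 12. The gap is 10 - 4 = 6 to 12 - 4 = 8 weeks, of which about 2 weeks are on DSF.

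**3. Elevation that lasts while DSF continues.** Onset u is assumed uniform on weeks 0-6.
- Onsets in weeks 0-4 are all found at week 4.
- Onsets in weeks 4-6 are exposed: (6 - 4)/6 = 33%. With a calendar month (4.35 weeks) it is (6 - 4.35)/6 = 27.5%.
- These are missed only if the value clears before T, that is, within 4-6 weeks of stopping DSF. If clearance takes longer, none is missed.

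If clearance after week 6 is exponential with mean m, P(detected) = 4/6 + (2/6) x exp(-(T - 6)/m).
- m = 2, T = 12: 0.667 + 0.333 x 0.050 = 68%.
- m = 4, T = 10: 0.667 + 0.333 x 0.368 = 79%.
- With weekly draws in weeks 1-6: 100%.

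**4. Transient elevation.** Duration is exponential with mean m from onset.
P(detected) = (m/6) x [1 - exp(-4/m) + exp(-(T - 6)/m) - exp(-(T - 4)/m)].
- m = 2, T = 12: (2/6) x [1 - 0.135 + 0.050 - 0.018] = 30%.
- m = 4, T = 10: (4/6) x [1 - 0.368 + 0.368 - 0.223] = 52%.
- With weekly draws: m x [1 - exp(-1/m)] = 79% (m = 2) and 88% (m = 4).

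For a fixed duration of d weeks, up to 4, the share missed is 1 - d/6:

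| Duration (weeks) | Missed |
|---|---|
| 1 | 83% |
| 2 | 67% |
| 3 | 50% |
| 4 | 33% |

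At 6 weeks it is 0% (T = 10) or 33% (T = 12).

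**5. Delay in the persistent case.** Mean time on DSF above the threshold before detection or end of RT is [(4 x 4/2) + (2 x 2/2)]/6 = 10/6 weeks = 11.7 days. With weekly draws it is 0.5 week = 3.5 days. The 90th percentile is 24 against 6 days.

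**6. Sensitivity of the escalation estimate.** One further DLT at 375 mg/day (3/10) gives about 26-28% there, above the 25% margin in 14.3.2, and about 15-17% at 250 mg/day. This shows how much one event weighs among 18 patients. It is not evidence that an event was missed.

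Weekly draws serve here only as a reference, because blood is already taken weekly for CBC.

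**The case against.** The schedule is stated consistently in four places, so the monthly frequency looks deliberate. Both hepatic DLTs were found under it, although the documents do not say at which visit or whether extra tests were done. Hepatitis is listed as rare (1.2.11), adverse events are reviewed weekly during RT, and 6.2.1 requires a work-up of any hepatic dysfunction. All of this stands. It limits the size of the problem but does not supply a liver value for weeks 5 and 6.

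Several stronger readings are tempting and are not supported.

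- **Most of the six weeks is unprotected.** This needs elevations of about 3 weeks or less that clear while DSF continues. The documents give no durations, and 1.2.10 describes hepatotoxicity as usually reversible once DSF is stopped early, which fits the persistent case better.
- **Up to 58 days without a result.** Adding the 30-day baseline allowance ("Baseline evaluations, labs and MRIs must be done no more than 30 days prior to the start of the protocol therapy") to the first 28 days counts time before the DSF-with-RT course starts. The interval on drug to the first draw is about 28 days.
- **The TITE-CRM time weighting is at fault.** The statement that "since previously published data shows that toxic events occur evenly throughout the time of the study we will not implement a weighting function" concerns the completed escalation phase. Once patients have full follow-up, the weighting no longer matters. A missed DLT would then bias any estimator.
- **The expansion dose decision is affected.** No expansion rule uses a DLT rate, the primary endpoint is OS, and 250 mg/day is already the dose during RT. In the check above, 250 mg/day is the level closest to 20% with one further DLT at either dose.
- **Patients stay on DSF through the whole gap.** The 4-6 weeks after RT lie between the two DSF courses.

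**Conclusion.** The concern holds in a limited form. Liver tests fall about once in the six weeks of DSF with RT, then not for 6-8 weeks, with none at the end of RT. Two kinds of hepatic DLT can go unrecorded: transient ones, and those that start in about the last two weeks (28-33% of the period) and clear before cycle 1. Earlier lasting elevations are detected late, not lost.

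Under uniform onset and a week-4 draw, detection is about 68-79% in the persistent case and 30-52% in the transient case. The persistent figure rises to 100% if clearance takes longer than the interval to cycle 1. Which case applies cannot be settled from the documents.

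The consequence is for the completeness of toxicity data, a secondary objective, and for applying 6.2.1. It does not reach the expansion phase's primary analysis or its dose. The change is worth making because it costs little.

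**What to change.** 1. Reconcile the liver-test timing in 5.5 and 10.2 note 6 with the laboratory DLT criteria in 5.9.2 and the condition in 6.2.1. Use blood already drawn for the weekly CBC and cover the end of RT. The sponsor sets the frequency and states which result satisfies 6.2.1. Doses, thresholds and stopping rules stay as they are.
2. Report the actual liver-test dates for the 18 escalation patients, including the visit at which each hepatic DLT was found.
3. Label the escalation hepatic DLT rate as based on monthly sampling, and show it separately from any more densely sampled expansion rate.

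**Cost.** A short amendment and a few extra laboratory tests. At the upper bound, with a test on all six weekly draws, this is 6 - 1 = 5 more per patient, or 5 x 15 = 75 over the planned additional patients. It would be fewer if some have already been treated, since current accrual is not stated. Denser sampling may raise the observed hepatic DLT rate and makes it less comparable with the escalation phase, which is why the rates should be shown separately.
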